## **1. METHODS**

### **2.1 Participants**

Veteran outpatients 18 to 50 years of age suffering from PTSD with and without depressive symptoms were recruited from the James A. Haley Veterans' Administration Hospital outpatient clinics and surrounding community. Participants were phone screened for safety and appropriateness of trial. In addition, the clinical information in the Veterans' Administration electronic medical records was reviewed. Veterans eligible to enroll and interested in participating in the study were scheduled for the initial screening/baseline visit and sent a copy of the informed consent. Those found to not be eligible or not interested in the study were referred to their primary mental health clinician or offered contact information for clinical care, if not already established with a provider.

Participants were required to meet all of the inclusion criteria in order to participate in this study, which included being male or female between the ages of 18-50 years. They had to meet DSM-5 criteria for PTSD as determined by clinical interview using CAPS for DSM-5 and have a PTSD checklist for DSM-5 (PCL-5) score greater than or equal to 45. Participants were also required to be on a stable medication regimen and psychotherapy for at least one month as well as be able to maintain this regimen for the duration of the treatment portion of the trial. The stability of the treatment regimen was assessed as part of the baseline history by an experienced psychiatrist. All participants had capacity to provide written informed consent. Candidates meeting any of the exclusion criteria at baseline were excluded from study participation. During the study, veterans could not be enrolled in an acute treatment of PTSD using evidence-based psychotherapy including Prolonged Exposure Therapy (PE), Cognitive Processing Therapy (CPT), or Eye Movement Desensitization and Reprocessing (EMDR). For safety reasons, the

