## **2.2 Procedures**

2.2.1 Overview: The screening/baseline visit began by acquiring written informed consent.

Subsequently, evaluations to determine safety and appropriateness, as well as clinical ratings and laboratory testing (Urine Drug Screen (UDS) and urine pregnancy testing) were performed.

Those meeting eligibility criteria, including ability to obtain motor threshold, were randomized to 1 Hz versus 10 Hz stratified by significant depression (Montgomery-Asberg Depression Rating Scale (MADRS) (Montgomery and Asberg, 1979) > 19). Participants were treated for 5

days a week for 6 weeks with a 3 week taper (3 treatments per week for 1 week, 2 treatments per week for 1 week, then 1 treatment per week for 1 week). Participants underwent clinical evaluation weekly for clinical effect during the treatment, at the end of the taper and at 1 and 3 months post treatment. In addition, safety was assessed prior to each treatment and/or evaluation.

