2.2.2 Screening/Baseline Visit: Participants first were informed about the study and given an opportunity to have all questions answered. When the veteran understood the protocol and was comfortable with participating, written consent was obtained. After consent, the Veteran underwent the following evaluations for safety and to confirm the appropriateness of entry into the trial: basic demographics; Transcranial Magnetic Stimulation and Safety Screen (TASS) (Keel et al., 2001); a history and physical by a TMS credentialed physician; and a UDS for all participants and a urine pregnancy test for all women of child-bearing potential. Clinical evaluations consisted of measures of PTSD, function, depression, traumatic brain injury (TBI), pain, and handedness with the Annette Handedness Scale (Annett, 1970). Clinician Administered PTSD Scale (CAPS-5) (Blake et al., 1995; Weathers et al., 2013) was used for baseline/screening as well as for post treatment evaluation. The CAPS-5 was developed by the National Center for PTSD and has become the "gold standard" for assessing PTSD in individuals over age 15. The evaluation provided a measure of symptom severity and sufficient criteria to determine whether a current diagnosis of PTSD was valid. The PCL-5 was used at the Screening/Baseline visit and during each Clinical Evaluation to assess PTSD symptoms (Blevins et al., 2015; Wortmann et al., 2016). This measure provided a minimum score for PTSD symptom severity as well as a secondary measure of PTSD symptoms. The functional status of veterans was measured using the Inventory of Psychosocial Functioning (IPF) (Rodriguez et al., 2012). The IPF was an 80

question self-report scale that assessed function in the areas of family, work, friendships and socializing, parenting, education, self-care, and romantic relationships with spouse or partner.

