### **2.3 Data Analysis**

Data were double entered into an Access database and cross checked for discrepancies prior to analysis. Discrepancies were resolved by returning to primary sources. Descriptive

statistics were reported for the demographic and clinical characteristics of the obtained sample, including age, sex, education, employment, baseline function (IPF), baseline severity of PTSD (CAPS and PCL-5), baseline depression (QIDS-SR, MADRS), baseline pain (Pain Score), and baseline post concussive symptoms (NSI). Categorical variables were expressed as frequencies with percentages, and continuous variables as means with standard deviations. To assess how well the samples were randomized, the two active treatment groups were compared on baseline variables including demographics and the outcomes. No missing data imputation was performed. Chi-square tests and Fisher's Exact Test (whenever cell count is less than 5) were used to compare categorical variables; *t-tests were* used to compare continuous variables within and between groups.

For the primary hypothesis, a Welch two-sample t-test that assumes unequal variances was used to investigate whether 1 Hz rTMS versus 10 Hz rTMS provides a significantly greater improvement in PTSD symptoms (CAPS score) and/or function (IPF score) by 30th treatment. Improvement in an outcome was primarily defined as change in scores from pre-treatment baseline to post 30 treatments. The presence of a significant improvement from baseline to post 30 within each treatment group was also tested by performing a paired t-test.

Secondarily, improvement was also evaluated as the proportion of responders and remitters by post 30 treatments. Response was defined as score reduction of 50% (QIDS-SR and MADRS) or 30% (PCL-5 and CAPS-5). Remission was defined using the following score thresholds: 5 or less for QIDS-SR; 10 or less for MADRS; 33 or less for PCL-5; and no longer meeting criteria of PTSD on the CAPS-5. Other secondary analyses were similarly performed on QIDS-SR, pain, NSI, MADRS and PCL-5 scores.

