Additionally, sustainability of these treatment effects was investigated using loess (local least square regression), a non-parametric approach suitable for smoothing our numerical vector, of repeated observations. Loess fits least squares regressions to localized subsets of outcome data to produce graphical description of nonlinear empirical relationships (Jacoby, 2000). The graphical displays included smooth curves plus 95% confidence bounds which allowed us to evaluate a statistically significant difference between the mean trajectory over time versus its starting baseline score. We preferred the loess method to the simple pointwise plot of estimates of the mean for two reasons: addition of pointwise 95% confidence intervals will result in less efficient use of data compared to the loess estimates that are based on regressions in local neighborhood of each time point; and an alternative use of standard error of the mean around each estimate is not appropriate for inference as it underestimates the variability between individuals within the study sample (Diong et al., 2018; Nagele, 2003).

The proportions of side effects and dropouts per group were captured. Given the low proportions, a nonparametric binomial test was used to test for significant group difference in their proportions. Two-sided p-values were calculated and used to assess statistical significance defined as  $p < 0.05$ . All statistical analysis was carried out using the R statistical application.

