### **3. RESULTS**

#### **3.1 Patient population**

Participant recruitment, enrollment, assignment to study conditions, and study retention are presented as a Consort diagram in Figure 1. Forty-four participants were enrolled with data

being acquired from September 2014 until February 2018. Nine veterans were not randomized with six failing to meet diagnostic criteria by CAPS-5, one was determined to have a history of seizures, one was unable to get off work, and one was unable to have motor threshold determined. Of the 35 randomized, 17 were allocated to the 1 Hz group and 18 to the 10 Hz group. Of the 17 veterans in the 1 Hz group, 14 completed the primary endpoint and all subsequent visits. The three participants who did not reach the primary endpoint included two that stopped due to work concerns and one who was lost to follow-up. Of the 18 veterans in the 10 Hz group, 13 completed the primary endpoints with one of those not completing the taper or follow-up visits. The five who did not reach the primary endpoint included two that could not tolerate the first treatment, one stopped due to headaches from another medical condition, one was too frustrated by parking, and one was lost to follow-up. A total of 27 who completed the primary end points constituted the final sample for testing the primary hypothesis, and they had no missing data on the tested outcomes.

- Figure 1 about here –

There were no significant differences between treatment groups on their baseline assessment scores, including demographic and baseline rating scales. (Table 1)

- Table 1 about here –

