### **3.5 Post-hoc power calculations**

Given that the final group sample sizes of 14 and 13 (see Figure 1) used to test our primary hypothesis fell short of our anticipated evaluable sample of 40, inadequate statistical power was suspected. Therefore, post-hoc power calculations were performed based on the statistics obtained from the results of t-tests for CAPS-5 (Table 2). Using a paired samples t-test with alpha of 0.05, there were 98% and 76% power (for 10 Hz and 1 Hz groups respectively) to reject the null hypothesis of no difference between the baseline and post-30 scores (that the mean of the paired differences is zero); which support the conclusions reached from our significant results. For the nonsignificant results of 1 Hz versus 10 Hz, however, there was low power to

reject the null hypothesis of no difference in group means using a two-sided two-sample unequal-variance t-test with alpha of 0.05. Therefore, no definitive conclusion can be derived from any failure to reject the null (i.e. non-significant findings) in this study. Although we did not find a definitive conclusion with our study, the preliminary results are that if a difference exists at the group level, it is not likely a large clinical difference.

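### Within-arm and pooled falls from baseline are uncontrolled change, because both arms are active and participants unmasked; they should not be called treatment effects or backed by post-hoc power

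*Combined protocol and SAP*

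**What the plan says.** Section 2.2.1 states that eligible veterans "were randomized to 1 Hz versus 10 Hz stratified by significant depression". Section 2.2.4 gives both groups the same number of active sessions and pulses, and says that participants and treaters knew the assignment while the raters of the clinician scales did not.

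Entry and baseline share one visit. Section 2.1 requires veterans to "have a PTSD checklist for DSM-5 (PCL-5) score greater than or equal to 45" and to meet PTSD criteria on CAPS-5. Section 2.2.2 then uses the same measures as outcomes: "The PCL-5 was used at the Screening/Baseline visit and during each Clinical Evaluation to assess PTSD symptoms", while the CAPS-5 "was used for baseline/screening as well as for post treatment evaluation".

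In 2.3 the primary analysis is a Welch test between arms. A within-arm test follows: "The presence of a significant improvement from baseline to post 30 within each treatment group was also tested by performing a paired t-test". The longitudinal analysis is introduced with the words "sustainability of these treatment effects was investigated using loess", and the curve is judged against its own starting score.

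Sections 3.2 and 3.3 are headed as effects. They report within-arm falls and a pooled PCL-5 fall lasting to 3 months. Section 3.5 gives within-arm post-hoc power on CAPS-5 of 98% (10 Hz) and 76% (1 Hz), "which support the conclusions reached from our significant results". Its closing caution covers only non-significant findings.

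**The concern.** A paired test against zero change asks whether scores moved, not why. With no inactive comparator, the movement combines any effect of rTMS with natural course, expectancy, frequent staff contact and some regression to the mean. Randomisation removes these from the difference between arms but not from the change within an arm or in the pooled sample.

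The positive efficacy statements in 3.2, 3.3 and 3.5 all rest on such change. The randomised contrast was null, and two active arms with a null contrast cannot separate both frequencies working from neither working. A reader who takes the within-arm results as treatment effects would draw a conclusion that the design cannot give. The post-hoc power sentence adds to this by appearing to offer independent confirmation.

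**Working it through.** **1. The plan's own power figure.** Inputs: 1 Hz group, n = 14, paired p = .03 on CAPS-5 (3.2); alpha 0.05 (3.5); two-sided p-values as the general rule (2.3).

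- Observed t with 13 df at two-sided p = .03: t = 2.436.
- Standardised change: 2.436 / √14 = 0.65.
- Post-hoc power = P(T > critical value), where T is noncentral t with 13 df and noncentrality 2.436.
- Two-sided critical value 2.160: power 61.6%. One-sided critical value 1.771: power 74.6%.
- Allowing for rounding of p (about 0.025 to 0.035): 59% to 65% two-sided, 72% to 77% one-sided.

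The stated 76% is therefore reproduced only as a one-sided calculation. Section 3.5 does not give the sidedness of the paired calculation. In both versions n, alpha and p are the only inputs, so the power figure carries no information beyond the p-value. The 98% for 10 Hz cannot be checked, because the table with its p-value and SD is not shown.

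**2. What the randomised comparison can say.** Section 3.2 gives p = 0.77 (CAPS) and p = 0.69 (IPF). With 14 and 13 analysed, a two-sided 0.05 test has 80% power only for a standardised difference of about 1.12. The contrast therefore does not show the frequencies to be equivalent. Even a precise null would not show that either one works.

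**3. How much selection on the PCL-5 could contribute.** The documents give no PCL-5 SD or retest correlation. Assumed: bivariate normal scores, SD 15, retest correlation r from 0.6 to 0.9, no true change. The excluded fraction q is taken from the trial's own screening account. Section 3.1 says "Nine veterans were not randomized with six failing to meet diagnostic criteria by CAPS-5", and the other three were excluded for seizure history, work and motor threshold. None of the 44 is listed as failing the PCL-5 cut-off.

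- Lower case: the 95% upper limit for 0 of 44 is 1 − 0.025^(1/44) = 8.0%, so q = 0.08.
- Upper case: all six CAPS-5 failures also counted as low PCL-5, 6/44 = 13.6%, rounded to q = 0.14.
- Expected fall = (1 − r) × SD × φ(a)/(1 − q), with a = Φ⁻¹(q).
- q = 0.08: a = −1.405, φ(a)/(1 − q) = 0.1487/0.92 = 0.162. Fall = 0.4 × 15 × 0.162 = 0.97 at r = 0.6, and 0.24 at r = 0.9.
- q = 0.14: a = −1.080, φ(a)/(1 − q) = 0.2226/0.86 = 0.259. Fall = 1.55 at r = 0.6, and 0.39 at r = 0.9.

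Simulating a paired t-test at n = 14 under the same settings gives a significant improvement in about 3% to 4% of trials at q = 0.08 and 4% to 6% at q = 0.14. The nominal rate in that direction is 2.5%.

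**4. CAPS-5.** This scale has no total-score cut-off. If the six failures are treated as the lowest 14% of CAPS-5 scores, selection is worth a standardised change of 0.06 to 0.12 under the same correlations. The observed 1 Hz value is 0.65.

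**The case against.** The strongest defence is that the text claims little. Section 2.3 defines improvement neutrally as change from baseline, 3.2 labels the within-arm tests secondary, and 3.5 states its null as a zero mean paired difference, which can be read as saying only that scores changed. There are also safeguards: clinician raters were masked to arm, acute evidence-based PTSD psychotherapy was excluded, a psychiatrist assessed regimen stability, and medication was held constant. The text ends at 3.5, so limitations may be discussed elsewhere.

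Much of this stands, and it lowers the severity. It does not remove the point. Section 2.3 does use the words treatment effects for the change, 3.2 and 3.3 are headed as effects, and 3.5 cautions only about non-significant results. Masking raters to frequency does not remove an expectation of improvement common to both arms, and the PCL-5 is self-reported by unmasked participants.

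A reader might go further and infer that selecting veterans at 45 or more produced the positive findings. A screened pool assumed to centre on 45 (SD 15, r = 0.8) would give a fall of about 2.4 points and false improvement in about 15% of trials at n = 14. The documents do not support that reading. Such a pool loses half its candidates at the cut-off, whereas 3.1 lists no one excluded on it. The p = .03 and the power figures are for CAPS-5, and selection accounts for little of that change. MADRS above 19 stratifies and does not exclude. The pooled result is a loess curve, so a false-positive rate for a pooled paired t-test would describe an analysis that the documents do not contain.

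**Conclusion.** The point holds as a matter of design and does not depend on the numerical assumptions: with two active arms, unmasked participants and no inactive comparator, change from baseline does not identify a treatment effect. The post-hoc power adds no evidence, and its 76% is about 62% under the two-sided rule in 2.3.

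Regression to the mean is a contributing reason, most directly for the PCL-5. Its size is roughly 0.2 to 1.6 points, with 3% to 6% false improvement at n = 14. This assumes SD 15, retest correlation 0.6 to 0.9 and 8% to 14% exclusion. Any selection at the phone screen in 2.1 is unknown, because the text does not say whether a PCL-5 was taken there.

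It should not be read as showing that rTMS had no effect, or that the falls are artefact; the design leaves both open. The randomised primary comparison is unaffected and was reported as null, so this should be fixed but is not critical.

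**What to change.** - In 2.3, label the paired tests and the pooled curves as descriptive change from baseline. Report mean change with a 95% confidence interval.
- In 2.3, replace the words treatment effects in the loess paragraph with change from baseline.
- In 3.5, delete the clause saying that within-arm power supports the conclusions.
- In 3.2 and 3.3, state that pre-post change may include natural course, expectancy and some regression to the mean, most directly for the PCL-5 with its entry cut-off of 45, and so is not evidence of efficacy. If a numerical bound is added, base it on the screening losses in 3.1 and state its assumptions.
- Separately, reconcile the mention of sham allocation cards in 2.2.4 with the two-active-arm design described elsewhere.

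The cost is wording plus confidence intervals from data already held; no new data are needed. The downside is that the report loses its claim of significant improvement as a treatment effect.

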The Montgomery-Asberg Depression Rating Scale (MADRS) (Montgomery and Asberg, 1979) and Quick Inventory of Depressive Symptomatology-Self Report version (QIDS-SR) (Rush et al., 2005; Rush et al., 2003) assessed the severity of depressive symptoms. The MADRS score was also used to stratify the randomization (MADRS > 19 for depressed group) as well as a secondary measure of depressive symptoms. The QIDS-SR assessed change in depressive symptoms during the trial. The QIDS-SR was administered during initial screening and during the Clinical Evaluation visits to track any change in depressive symptomatology. In addition, a physical pain score was obtained at baseline/screening and at every Clinical Evaluation. The participant was asked to rate overall physical pain in the last 24 hours on a scale of 0 to 10, with 0 corresponding to no pain and 10 corresponding to the most severe pain ever experienced. The Neurobehavioral Symptom Inventory (NSI) (King et al., 2012) assessed possible post-concussive symptoms associated with mild TBI. The scale is a 22 item self-report measure.

2.2.3 Evaluations: A safety assessment was performed prior to each treatment or at any time clinically indicated (e.g., significant side effect during or between treatments) consisting of asking about: 1) side effects, 2) changes in medication, 3) changes in medical conditions, and 4) changes in psychiatric symptoms (e.g., suicidality, plans to harm others). The Clinical Evaluations were performed after every 5 treatments for first 30 treatments, at the end of treatment taper, and at 1 and 3 month post-treatment follow-ups. The Clinical Evaluations consisted of PCL, QIDS-SR, and pain score on every evaluation visit. The IPF was obtained at baseline, after 15 treatments, after 30 treatments, at the end of treatment, and at the post

treatment 1 and 3 month follow-ups. CAPS, MADRS, and NSI were obtained at baseline/screening and after the 30th treatment.

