2.2.4 Repetitive Transcranial Magnetic Stimulation: The veterans were placed in the NeuroStar chair (Neuronetics, Malvern, PA) with hearing protection in place, and the motor threshold (MT) was determined. The MT was defined as the stimulus intensity of stimulation that induces visually perceptible movement of the contralateral (in this case, the left) abductor pollicis brevis (APB) 50% of the time. (Pridmore et al., 1998). Once the spot of maximal contraction was determined, a PEST algorithm (Mishoury et al., 2004) was used to determine the MT four times. The mean of these four MT served as the MT used in the study. After motor threshold determination, a stratified randomization was performed based on significant depressive symptoms, which were defined as a MADRS score > 19. Using a computer randomization schedule, an investigator who was independent of any treatments generated two random lists of active and sham index cards (i.e., with and without significant depression) that were placed in envelopes prior to the trial beginning. When the participant was ready to begin the first treatment, the treater opened the next envelope in line for the appropriate group to determine the randomization assignment. The participant knew the assignment as well as the treater but the investigators assessing all the clinician rating scales were masked to assignment.

After the randomization, the stimulator coil was positioned over the dorsolateral prefrontal cortex - DLPFC (Brodmann Area 9/46). The right dorsolateral prefrontal cortex was targeted using head measurements and a computerized program that provides coordinates for the approximate F4 electrode site under the 10/20 electrode convention (Beam et al., 2009). The dose of rTMS over the DLPFC was 110% of MT. The intensity of 110% MT was chosen as our sample was limited to 18-50 years of age. The 110% MT was thought to be a reasonable option

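### MADRS and QIDS-SR remission is an end score with no baseline condition, so a veteran who entered at or below the cut-off counts as a remitter without improving

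*Combined protocol and SAP*

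**What the plan says.** Section 2.1 describes the population as veterans "suffering from PTSD with and without depressive symptoms". The entry criteria there set a floor for PTSD severity (a PCL-5 of at least 45 and a DSM-5 diagnosis using the CAPS), but none for MADRS or QIDS-SR.

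Section 2.2 uses the MADRS only to stratify ("MADRS > 19 for depressed group"). Section 2.2.4 describes two randomisation lists, "i.e., with and without significant depression", so veterans with MADRS of 19 or less are enrolled and randomised by design.

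Section 2.3 then says that "improvement was also evaluated as the proportion of responders and remitters by post 30 treatments". Remission on the depression scales is "5 or less for QIDS-SR; 10 or less for MADRS". On the PTSD scales it is a PCL-5 of 33 or less, and no longer meeting PTSD criteria on the CAPS-5. Response is a relative fall: "Response was defined as score reduction of 50% (QIDS-SR and MADRS) or 30% (PCL-5 and CAPS-5". No baseline condition, subset or denominator is stated for any of these rates.

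**The concern.** Remission is offered as evidence of improvement, yet on two of the four scales it can be met with no improvement. A veteran who enters with a MADRS of 8 and leaves with 8, or worsens to 10, is a remitter. The same holds for a QIDS-SR that starts and stays at 5 or less.

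Three things follow if such veterans are in the analysis. The remission rate is inflated in each arm that contains them. A real difference between 1 Hz and 10 Hz is diluted, because these veterans count as remitters whatever the treatment does. With 14 and 13 completers, a few more of them in one arm can look like a treatment difference.

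**Working it through.** **1. Cut-offs against entry criteria.** The plan states no remission figure that can be reproduced, because the counts are in Table 3, which is not in the available text. The first check is therefore logical.

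| Scale | Remission (2.3) | Entry floor (2.1) | Can a veteran enter already in remission? |
|---|---|---|---|
| PCL-5 | 33 or less | 45 or more | No |
| CAPS-5 | PTSD criteria no longer met | PTSD diagnosis required | No |
| MADRS | 10 or less | none | Yes; 0 to 10 lies inside the stratum at 19 or less |
| QIDS-SR | 5 or less | none | Yes |

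On the PTSD scales remission requires change. On the depression scales it does not.

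**2. Inflation.** There are 27 completers (section 3.1). Let *k* of them start at or below the cut-off and stay there, and let *r* be the true remission rate in the rest. Both are assumptions.

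Observed rate = (*k* + *r*(27 − *k*)) / 27.

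- With *r* = 0 and *k* = 1, 3, 5, 8: 3.7%, 11.1%, 18.5%, 29.6%.
- With *r* = 20% and *k* = 0, 3, 5, 8: 20.0%, 28.9%, 34.8%, 43.7%.

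**3. Dilution.** Let a share *f* of each arm be already at or below the cut-off and remain so. Observed rate = *f* + (1 − *f*)*p*, so the gap is multiplied by (1 − *f*). Assume true rates of 20% v 50%, a gap of 30 points.

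| *f* | Lower arm | Higher arm | Gap |
|---|---|---|---|
| 10% | 28% | 55% | 27 points |
| 20% | 36% | 60% | 24 points |
| 30% | 44% | 65% | 21 points |

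Exact power of Fisher's test (two-sided 0.05, arms of 14 and 13, the same 20% v 50%) is 32% with nobody affected. With 2 such veterans per arm it is 15% if they are counted and 27% if they are left out. With 4 per arm it is 8% and 18%.

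**4. Chance imbalance.** Allocate *k* such veterans at random to arms of 14 and 13, ignoring stratification. If *x* fall in the arm of 14, the spurious gap is *x*/14 − (*k* − *x*)/13, with *x* hypergeometric.

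| *k* | SD of gap | Gap of 15 points or more, either way | Fisher p < 0.05 from imbalance alone |
|---|---|---|---|
| 3 | 12 points | 22% | 0% |
| 5 | 15 points | 33% | 4.1% |
| 8 | 18 points | 42% | 3.3% |

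For MADRS these are upper-end illustrations. Every veteran at 10 or less sits in the same randomisation stratum, so balanced lists would reduce the gap.

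**5. Response.** A 50% fall is required, so an unchanged score cannot be a response. The remaining weakness is minor: from a low start a few points suffice (MADRS 6 to 3), and a baseline of 0 leaves the percentage undefined.

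**The case against.** The strongest reply is that no harm has been shown. Section 2.3 names no denominator, and Tables 1 and 3 are not in the available text, so the rates may have been computed in a subset, or no completer may have started below a cut-off. The 10% to 30% range has no support in the documents. This stands as a limit on size. It does not rescue the definition, which misclassifies such veterans when applied as written.

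Stratification is a fair reply to the imbalance figures, though a partial one. The split is at MADRS 19, not 10. QIDS-SR is not a stratification factor, blocking is not described, and 8 of the 35 randomised did not reach the endpoint (section 3.1). The dilution figures assume equal shares in the arms and so do not depend on chance imbalance.

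It is also true that these are secondary rates, that the group comparison was null (section 3.2), that section 3.5 already declines to draw a definitive conclusion from non-significant results, and that power stays low after the correction. The step 4 figures show no excess of significant results from imbalance alone.

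A reader might infer three stronger things that the documents do not support:

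- That every veteran classed as not depressed is an automatic remitter. Those at MADRS 11 to 19 must still improve.
- That response is equally empty. It requires a 50% fall.
- That dilution explains the null remission result. The number affected is unknown.

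**Conclusion.** The concern holds for remission on MADRS and QIDS-SR. The definition and the entry criteria together let a veteran be counted as a remitter without improving, and nothing else in the plan prevents it. The direction is known for a given number of such veterans: remission is inflated wherever they fall, and a true difference is diluted when they are spread over both arms.

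The size is not known and could be zero. If 10% to 30% of completers were affected and stayed at or below the cut-off, a 30-point contrast would fall to between 27 and 21 points. Both the shares and the 20% v 50% contrast are assumptions. The consequence is confined to secondary rates; the primary comparison of CAPS and IPF change is unaffected.

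**What to change.** - In section 2.3, count MADRS remission only in participants with baseline MADRS above 10, and QIDS-SR remission only in those with baseline QIDS-SR above 5.
- In Table 3, give the denominator per arm for each rate and the number per arm already at or below each cut-off at baseline. If that number is zero, this line settles the matter.
- Keep the continuous MADRS and QIDS-SR change scores for all participants.
- Leave the response definition as it is. At most, report each scale's response in the same denominator as its remission, so that the paired rates describe the same people. Restricting QIDS-SR response by the MADRS stratum would drop veterans on the strength of a different scale.

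Both scales were collected at baseline and after the 30th treatment (section 2.2.3), so the work is two added conditions and a re-run of Table 3. The cost is smaller denominators in an already small trial. A fall from 11 to 10 on the MADRS would still count as remission, which is one reason to keep the change scores alongside. Because results are already known, the restricted rates should be labelled as specified afterwards, although the restriction uses baseline values only.
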